6.3.2. Additional considerations

All analyses will be repeated for each age subgroup.

- To complement the analysis of persistence, a thorough description of NT waning from year 1 after the first booster dose up to 15 years will be presented for the set of subjects completing the entire 15-year follow-up with no protocol deviations, including those receiving a second booster dose within the previous clinical studies and current study; for those ones, a constant value of NT = 1 from the post booster visit will be used in the analysis.
- Analysis of boostability will be presented both by time-point (i.e. for each unscheduled visit separately) and aggregated (i.e. all visits considered together).
- Depending on the amount of missing data and as a form of sensitivity analysis, a repeated measure model could be used to evaluate the GMTs persistence.

6.4. Analysis of safety

6.4.1. Analysis of safety planned in the protocol

In this study, only serious adverse events (SAEs) and pregnancies will be collected.

For vaccinated subjects:

- All pregnancies after vaccination until study end.
- All SAEs will be collected for 1 month after vaccination.
- SAEs leading to study withdrawal

In addition to the above-mentioned reporting requirements and in order to fulfil international reporting obligations, SAEs that are related to study participation (i.e. protocol-mandated procedures, invasive tests, a change from existing therapy) or are related to a concurrent GSK medication/vaccine will be collected and recorded from the time the subject consents to participate in the study until she/he is discharged from the study.

CONFIDENTIAL

205847 (TBEV POLYGELINE FREE-025 EXT:021)

Statistical Analysis Plan Final

An overview of the protocol-required reporting periods for SAEs and pregnancies is given in the table below.

Event	scheduled BD Visit 23*	unscheduled V Visit 24, 25, Visit 23.1, 24.1, 25.1 26 or 27	unscheduled BD 21 days after vaccination or 26.1	Study conclusion visit: Visit 23.2, 24.2, 25.2 or 26.2
SAEs leading to withdrawal from the study				
SAEs related to study participation or concurrent GSK medication/vaccine				
SAEs ¹				
Pregnancies ²				

*Informed consent obtained before events described below are collected.

V: vaccination; BD: blood draw

¹In vaccinated subjects all SAEs will be collected for 1 month after vaccination.

² In vaccinated subjects all pregnancies after vaccination until study end

6.4.2. Additional considerations

6.4.2.1. Exclusion of implausible solicited Adverse Event

Not applicable.

6.4.2.2. Solicited Adverse Events

Not applicable.

Safety completeness analysis

Not applicable.

6.4.2.3. Unsolicited Adverse Events

This analysis applies to all SAEs occurring during the study and related to the study participation or to a concurrent GSK medication/vaccine; additionally, for subjects receiving a booster dose, all SAEs, judged either as probably related, possibly related, or not related to vaccination by the investigator, will be recorded in AE CRF, with a start date on or after the date of booster dose.

The original verbatim terms used by investigators to identify adverse events in the CRFs will be mapped to preferred terms using the MedDRA dictionary. The serious adverse events will then be grouped by MedDRA preferred terms into frequency tables according to system organ class.

All reported SAEs, as well as SAEs judged by the investigator as at least possibly related to study vaccine, will be summarized according to system organ class and preferred term within system organ class. When an SAE occurs more than once for a subject, the maximal severity and strongest relationship to the vaccine group will be counted.

Separate summaries will be produced for the following categories:

- Serious adverse events.
- Serious adverse events that are possibly or probably related to vaccine.
- Serious Adverse event leading to withdrawal.
- Deaths

Data listings of all serious adverse events and pregnancies will be provided by subject

6.4.2.4. Combined Solicited and Unsolicited Adverse Events

Not applicable.

6.4.2.5. Clinical Safety Laboratory Investigations

Not applicable.

6.4.2.6. Concomitant Medication

Medications will be coded using the GSKDRUG dictionary.

The frequencies and percentages of subjects reporting concomitant medications will be tabulated by vaccine schedule and separated for scheduled and unscheduled visit

7. ANALYSIS INTERPRETATION

Comparative analyses will be descriptive with the aim to characterise the difference in immunogenicity between groups. No formal statistical comparison will be made.

8. CONDUCT OF ANALYSES

8.1. Sequence of analyses

Annual listings reporting subjects NT titres will be produced and made available to the investigators. Every year, any subject whose NT titre falls below 10 will be offered a second booster vaccination with *Encepur Adults*.

Final analysis will be conducted after completion of the immunogenicity evaluation at year 15, when the CSR will be produced.

A clinical study report containing all data will be written at study end.

Description	Analysis ID	Disclosure Purpose (CTRS=public posting, SR=study report, internal)	Dry run review needed (Y/N)	Study Headline Summary (SHS)requiring expedited communication to upper management (Yes/No)	Reference for TFL
Immunogenicity analysis year 11	IMM11y	Internal	N	No	16.2.6.1
Immunogenicity analysis year 12	IMM12y	Internal	N	No	16.2.6.1
Immunogenicity analysis year 13	IMM13y	Internal	N	No	16.2.6.1
Immunogenicity analysis year 14	IMM14y	Internal	N	No	16.2.6.1
Final analysis year 15	Final	Study report	Y	Yes	All tables and listings in the TOC

8.2. Statistical considerations for interim analysis

The annual evaluations will simply have an informative purpose, evaluating on a yearly basis the subjects who will need a second booster dose. No further statistical considerations need to be applied.

9. CHANGES FROM PLANNED ANALYSES

Not applicable.

10. LIST OF FINAL REPORT TABLES, LISTINGS AND FIGURES

The following group names will be used in the TFLs, to be in line with the T-domains:

Group order in tables	Group label in tables	Group definition for footnote
1	C	Conventional
2	R	Rapid
3	AC	Accelerated Conventional

The following sub-group names for age class will be used in the TFLs

Sub-group order in tables	Sub-group label in tables	Sub-group definition for footnote
1	25-49Y	25-49 years old subjects
2	>=50Y	>=50 years old subjects
3	>=60Y	>=60 years old subjects

11. ANNEX 1 STANDARD DATA DERIVATION RULE AND STATISTICAL METHODS

11.1. Statistical Method References

The exact two-sided 95% CIs for a proportion within a group will be the Clopper-Pearson exact CI [Clopper CJ, Pearson ES. The use of confidence or fiducial limits illustrated in the case of binomial. *Biometrika*. 1934;26:404-413].

The standardised asymptotic two-sided 95% CI for the group difference in proportions is based on the method described in the following paper: Robert G. Newcombe, interval estimation for the difference between independent proportions: comparison of eleven methods, *Statist Med*. 1998; 17, 873-890]. The standardised asymptotic method used is the method six.

11.2. Standard data derivation

NV legacy

The incomplete date derivations are as follow for an event with start and stop date:

For an incomplete start date, if the day is missing while the month and year are available:

- when the month and year are identical to a complete stop date then the start date is imputed to the stop date.
- when the month and year are not identical to a complete stop date then the start day is imputed to the first day of the month.

For an incomplete start date, if the day and month are missing while the year is available:

- when the year is identical to a complete stop date then the start date is imputed to the stop date.
- when the year is not identical to a complete stop date then the start day/month is imputed to 01Jan.

For an incomplete stop date, if the day is missing while the month and year are available:

- when the month and year are identical to a complete start date then the stop date is imputed to the start date.
- when the month and year are not identical to a complete start date then the stop day is imputed to the first day of the month.

For an incomplete stop date, if the day and month are missing while the year is available:

- when the year is identical to a complete start date then the stop date is imputed to the start date.
- when the year is not identical to a complete start date then the start day/month is imputed to 31dec.

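### The partial-date rule in SAP 11.2 ignores the booster date, so some SAEs that follow the second booster can be dated before it and drop out of the post-booster summary

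*SAP*

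**What the plan says.** SAP 11.2 opens its rules with "The incomplete date derivations are as follow for an event with start and stop date". For start dates there are four branches.

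- Day missing, complete stop date in the same month: "when the month and year are identical to a complete stop date then the start date is imputed to the stop date".
- Day missing, no such stop date: "then the start day is imputed to the first day of the month".
- Day and month missing, complete stop date in the same year: "when the year is identical to a complete stop date then the start date is imputed to the stop date".
- Day and month missing, no such stop date: "when the year is not identical to a complete stop date then the start day/month is imputed to 01Jan".

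None of the branches refers to the booster date.

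SAP 6.4.2.3 and Protocol 10.8.3 describe two sources of SAEs for the analysis. SAEs related to taking part in the study, or to another sponsor product in use at the time, enter whenever they occur. For boosted subjects, all other SAEs are added "with a start date on or after the date of booster dose". Protocol 8.3.1 limits this fuller collection to one month after vaccination. SAP 6.4.2.3 also provides for a by-subject listing of every SAE. No other section sets a different rule for a partial date in the month of the booster.

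**The concern.** The analysis depends on whether an SAE began before or after the booster, but the rule that completes the date does not use the booster date. An event known to have begun in the booster month, on an unknown day, can be given a date earlier than the injection.

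SAE incidence is the only safety measure (Protocol 10.2, SAP 4.2), and it serves a secondary objective. With a collection window of one month, an error of a few weeks decides whether an event counts. Long-lasting and unresolved events are the ones most exposed.

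The number boosted is not given; Protocol 4.1 says that it cannot be estimated. If it were 10, 20 or 50 (assumptions), losing a single subject's only SAE would change the reported incidence from 10%, 5% or 2% to 0%.

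**Working it through.** The documents state no figure on this point, so there is none to reproduce. The four branches were applied literally.

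**Worked cases, booster on 15 March, start day missing**

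| True onset | Stop date | Imputed start | Relative to booster |
|---|---|---|---|
| 20 March | 27 March | 27 March | 12 days after |
| 20 March | 5 April | 1 March | 14 days before |
| 20 March | none complete | 1 March | 14 days before |
| 3 April | 9 May | 1 April | 17 days after |
| 10 March | 20 March | 20 March | 5 days after, although onset was before |
| 10 April | 28 April | 28 April | 44 days after, although onset was day 26 |

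An SAE is moved before the booster only when three things hold together: onset is in the booster month, the booster was not given on the 1st, and no complete stop date falls in that month. A stop date that itself lacks its day is not complete, so an event with both days missing in the booster month also goes to the 1st.

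**Share moved, day missing**

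Inputs:
- Booster on each day from 1 February to 31 May, 120 dates. This is an assumption based on Protocol 1.4.1, which expects autumn blood draws and vaccination 4 to 7 months later.
- Onset on each of days 0 to 30 after the booster, for the one-month window.
- Fixed event durations of D days (assumption).

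This gives 120 × 31 = 3,720 combinations. In a month of L days, the number moved is D·L − D(D+1)/2, up to a ceiling of L(L−1)/2 once D is L−1 or more. The four months have L = 28, 31, 30 and 31, which sum to 120.

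| Duration D | Number moved | Share of 3,720 |
|---|---|---|
| 0 days | 0 | 0% |
| 3 days | 3×120 − 4×6 = 336 | 9% |
| 7 days | 7×120 − 4×28 = 728 | 20% |
| 14 days | 14×120 − 4×105 = 1,260 | 34% |
| 30 days or more, or no complete stop date | 378 + 465 + 435 + 465 = 1,743 | 47% |

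Spreading boosters over the whole year hardly changes these shares; the ceiling becomes 47.5%.

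**Share moved, day and month missing**

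For February to May boosters the share is 0% when a complete stop date falls in the same year, as it does for every finite duration tried (up to 60 days). It is 100% when there is no complete stop date, because 01Jan precedes every booster. Over the whole year the figures are 0% to 16% for finite durations and 96% with no complete stop date.

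**The opposite error**

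The stop-date branches move starts later. With February to May boosters, they place a true post-booster SAE more than 30 days after the booster in up to 25% of day-missing cases (14-day duration), and in up to 100% of cases with day and month missing (60-day duration).

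**Check of the remedy**

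The start was set to the booster date whenever the known month and year (or year) matched the booster, and to the stop date if that came earlier. The share of post-booster SAEs dated before the booster was then 0% for durations of 0, 7 and 30 days and for no complete stop date, both for February to May and for the whole year.

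**The case against.** The strongest reply is that the plan never says an SAE is removed because of its imputed date. The start-date clause ends a sentence about what is recorded on the case report form. The tabulation sentence speaks of all reported SAEs, and SAP 5.1 defines the safety population by subject. This stands in part: the filter is an inference. It is still the natural reading, since that clause is the only text that says which further SAEs of boosted subjects belong to the analysis.

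Second, partial SAE dates should be rare. Reports are due within 24 hours (Protocol 8.4.1), the investigator reviews hospital records (8.3.3.1), a visit follows 21 days after the booster, and entries are verified against source (11.3). This stands. It applies most strongly to a missing month, since such an event could hardly be placed in a one-month window.

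Third, the rule is headed for events with both a start and a stop date, so it may not cover ongoing SAEs at all. This also stands, but it leaves those SAEs with no stated rule instead of a safe one.

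A reader might go further and infer that the rule always favours the vaccine, or that 47% (or 96% to 100%) of partly dated SAEs are lost. The documents do not support either. The worked case with onset on 10 March goes the other way, and those percentages are upper figures that require a long event or no complete stop date. Nor is every affected SAE lost from the analysis: those related to study participation or to a concurrent sponsor product enter whatever their date, and all SAEs stay in the listings.

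**Conclusion.** The gap is real but narrow. An SAE that follows the booster in the same month, with its start day missing and no complete stop date in that month, is dated before the booster. It then leaves the post-booster summary if the start-date clause is applied as a filter. The share affected among day-missing post-booster SAEs runs from 0% to 47%, rising with duration, under the assumptions of February to May boosters and onset spread evenly over days 0 to 30. The 01Jan branch matters only when the month is unknown too and no complete stop date falls in that year.

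The direction of error is not uniform across the rule. The expected number of affected SAEs cannot be computed, because the documents give neither the frequency of partial dates nor the number boosted; it is probably small. The point concerns only the safety summary and leaves the persistence and boostability analyses untouched. It is worth correcting because one event may determine the reported incidence.

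**What to change.** Add to SAP 11.2, for boosted subjects: if the known part of an SAE start date is compatible with onset on or after the second booster (same month and year, or same year when the month is missing), impute the booster date, unless a complete stop date precedes the booster. State that this also covers ongoing SAEs and SAEs with a partial stop date. Keep the present rule otherwise.

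The cost is a short addition to the SAP and a small programming change before the final analysis. The downside is that an occasional pre-booster SAE will be counted as post-booster, which is the conservative direction for a safety summary.

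One limit remains. A day-missing SAE that starts in a month after the booster month can still be moved to its stop date, as in the 10 April case above. The SAP should therefore also say whether the start-date clause and the one-month limit are applied to imputed dates when the SAE tables are built.

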##### **For all subjects:**

- Any investigational or non-registered product (drug or vaccine) other than the study vaccine used during the study period.
- Immunosuppressants or other immune-modifying drugs defined as follows:
  - Systemic administration of corticosteroids (PO/IV/IM) for more than 14 consecutive days within 90 days prior to all blood draws. This will mean prednisone  $\geq 20$  mg/day (for adult subjects), or equivalent. Inhaled and topical steroids are allowed.
  - Administration of antineoplastic and immuno-modulating agents or radiotherapy within 90 days prior to all blood draws.
- Received immunoglobulins or any blood products within 180 days prior to blood draw.
- Administration of long-acting immune-modifying drugs administered at any time during the study period (e.g. infliximab).

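### The last partial stop-date rule in SAP 11.2 overwrites a complete start date with 31 December, and the stop-date rules disagree on direction

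*SAP*

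**What the plan says.** SAP 11.2 introduces its partial-date rules with "The incomplete date derivations are as follow for an event with start and stop date". No other partial-date rule appears in the SAP. Under the heading for an incomplete stop date there are four rules:

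1. Day missing, same month and year as the start: "when the month and year are identical to a complete start date then the stop date is imputed to the start date".
2. Day missing, different month or year: "then the stop day is imputed to the first day of the month".
3. Day and month missing, same year as the start: "when the year is identical to a complete start date then the stop date is imputed to the start date".
4. Day and month missing, different year: "when the year is not identical to a complete start date then the start day/month is imputed to 31dec".

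Three other parts of the plan depend on dates. SAP 6.4.2.3 takes SAEs of boosted subjects whose start is on or after the booster date. Protocol 6.7.2 lists treatments that may cost a subject per-protocol evaluability, among them "Systemic administration of corticosteroids (PO/IV/IM) for more than 14 consecutive days within 90 days prior to all blood draws" and "Administration of antineoplastic and immuno-modulating agents or radiotherapy within 90 days prior to all blood draws", with a 180-day window for immunoglobulins and blood products. SAP 5.2.2.1 has elimination code 230/2040 for forbidden medication.

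**The concern.** Rule 4 sits under the stop-date heading and applies when the start date is complete, yet it changes the start. A programmer who follows the text discards a recorded onset and still has no stop date. Onset relative to the booster is what places an SAE in the post-booster summary, so a false onset can put an event on the wrong side of that line.

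Reading stop for start removes that error but leaves the set inconsistent. Rules 1 to 3 choose the earliest stop that the known part allows. Rule 4 then chooses the latest. The SAP gives no reason for the change of direction. If the same dates also feed the medication criteria, a duration or a gap to a blood draw could turn on which part of the date was missing.

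**Working it through.** The documents give no figure on this point to reproduce. The rules come from SAP 11.2. The calendar dates and course lengths below are assumptions, and durations count both end days.

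**Step 1. Rule 4 read literally, onset before the booster.** Assume a booster on 1 April 2019, an event starting 10 February 2019 and a stop recorded as 2020.
- True onset: 18 (to 28 February) + 31 (March) + 1 = 50 days before the booster.
- Imputed onset: 31 December 2019, which is 274 days after 1 April 2019.
- The event now passes the SAP 6.4.2.3 filter, and its stop date is still incomplete.

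This crossing needs an onset in the same calendar year as the booster. Protocol 1.4.1 expects autumn draws. Taking 1 September to 30 November, with the booster 182 days later (minus 60, plus 30), boosters fall from about 1 January to 30 June, so such onsets are possible.

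**Step 2. Rule 4 read literally, onset after the booster.** Same booster, onset 15 April 2019 (day 14), stop 2020. The onset becomes day 274. Over the booster range in step 1, 31 December lies 184 to 364 days after the booster. The move is always later, so the on-or-after filter is still met.

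**Step 3. Direction of the rules, with rule 4 read as stop.**

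| Start | Known part of stop | SAP stop | SAP duration | Latest possible stop | Longest true duration |
|---|---|---|---|---|---|
| 3 Mar 2019 | Mar 2019 | 3 Mar 2019 | 1 | 31 Mar 2019 | 29 |
| 20 Feb 2019 | Mar 2019 | 1 Mar 2019 | 9 + 1 = 10 | 31 Mar 2019 | 9 + 31 = 40 |
| 20 Nov 2018 | Jan 2019 | 1 Jan 2019 | 11 + 31 + 1 = 43 | 31 Jan 2019 | 11 + 31 + 31 = 73 |
| 20 Nov 2018 | 2019 | 31 Dec 2019 | 11 + 31 + 365 = 407 | 31 Dec 2019 | 407 |

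The last two rows have the same start. If the true stop was 10 January 2019, the course lasted 11 + 31 + 10 = 52 days. It is recorded as 43 when the month is known and as 407 when it is not.

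**Step 4. Conditional check: if these dates were used for the corticosteroid criterion (more than 14 days).** The rules were applied to all 365 start dates in 2019. The table gives the share of qualifying courses imputed to 14 days or fewer.

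| True length (days) | Stop day missing | Stop day and month missing |
|---|---|---|
| 15 | 96.7% | 96.2% |
| 21 | 77.0% | 94.5% |
| 28 | 54.0% | 92.6% |
| 30 | 47.4% | 92.1% |
| 42 | 7.9% | 88.8% |
| 60 | 0% | 83.8% |
| 90 | 0% | 75.6% |

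With a missing stop day imputed to the last day of the month, none of the 365 start dates gives 14 days or fewer at any of these lengths.

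For the 90-day window, a course starting 5 January 2019 with stop 2019 is imputed to end that same day. That is 269 days before a 1 October draw, even if treatment ran to 30 September.

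These shares are conditional on a partial stop date. They say nothing about how often one occurs.

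**The case against.** The strongest reply is that rule 4 contains a one-word slip which no competent programmer would follow: the heading concerns stop dates, and the parallel start-date rule uses 1 January. That is probably right about intent. It does not justify leaving an operative rule wrong, and it does not explain why rules 1 to 3 point the other way.

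The record needed for step 1 is also rare. The event must run into a later calendar year and have a stop known only to the year, while Protocol 8.4.3 and 8.5.1 require SAE reporting within 24 hours and follow-up to outcome. Before the booster, only SAEs related to study participation or to a concurrent GSK product are collected. This stands, and it keeps the point small.

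A reader might infer three stronger things that the documents do not support:

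- **That a post-booster SAE would be lost from its one-month window.** One month is the collection period. The analysis filter in SAP 6.4.2.3 has no upper limit, all reported SAEs are summarised, and step 2 shows that the event still passes.
- **That the rules always shorten durations.** Rule 4 read as stop lengthens them. The start-date rules can too, by using the first of the month or 1 January.
- **That immunosuppressant courses in general look too short to count.** Only systemic corticosteroids carry a duration threshold. Other agents and blood products count by 90-day or 180-day windows, and long-acting agents count at any time.

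On the per-protocol set, Protocol 6.7.2 says only that such treatment may affect evaluability. Protocol 6.7.1 has sites record, for all subjects, corticosteroid courses that already meet the criterion. That protection is not complete: for boosted subjects, nearly all medication from 7 days before to 28 days after the booster is also recorded.

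Latest-date imputation has its own error. A course of 3 to 5 March with stop March would count as 29 days instead of 3.

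**Conclusion.** The point holds as a drafting error and an inconsistency in SAP 11.2. As written, rule 4 produces a false onset, leaves the stop date missing, and can move a pre-booster event into the post-booster summary. Read as stop, it conflicts in direction with the other three rules. An effect on per-protocol membership is a possibility only: it requires that imputed dates feed code 230/2040, which neither document states, and site-level recording limits it.

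The size is small. The documents give no frequency of partial dates, few records are likely to be affected, and nothing in the design or the titre data depends on the rule. It is worth correcting because the change is easy and the text is wrong on its face.

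**What to change.** In SAP 11.2:

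- In the last stop-date rule, replace start with stop.
- Impute a partial stop date to the last day of the known month, or to 31 December of the known year, capped at last contact or study end.
- State that a complete date is never overwritten.
- State which derivations use imputed dates. If medication-based elimination (code 230/2040) is one of them, say so.

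The cost is a few lines of SAP text and the matching programming. The downside is that a few short courses may be counted as longer than they were. If the dates are used for elimination, a few more subjects may then leave the per-protocol set.
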